- Cognitive impairment (documented in medical record and/or MIS-T score of less than 4);
- ACT therapy within the past year;
- Inability to attend workshop prior to surgery;
- Imminent risk of suicide (including recent, related hospitalization);
- Indicated surgery is revision of TKA

Termination

Participants will be terminated from the study if they do not have surgery within approximately one year of attending workshop

Re-approaching Potential Participants

Consented participants who do NOT meet inclusion criteria before their surgery may be rescreened, re-approached, re-consented and reassessed for eligibility if they are indicated to have a second TKA surgery before the end of the study enrollment period. These participants will be eligible for this reassessment no earlier than eight weeks after their first TKA.

Data Analysis

Descriptive statistics (means, medians, percentages, standard deviations, and inter-quartile ranges) of all variables will be computed for each intervention group. We will describe sex and race/ethnicity results separately to identify potential differences, based on these biological variables. The distributions of continuous variables will be evaluated for normality. If data are non-normal, statistical analyses appropriate for non-normal data will be utilized (see below). Variables will be compared across intervention groups using a t-test for continuous variables, Wilcoxon-rank sum test for ordinal and non-normally distributed continuous variables, and Pearson Chi-square test for categorical variables. Variables that are found to significantly differ between the groups will be used as covariates in the comparison of outcome measures between the treatment groups.

Intent-to-treat (ITT) analyses will be conducted to assess treatment efficacy on post-operative outcomes using all subjects that have been randomized and had surgery performed. Only those who receive surgery are included in these analyses to test the efficacy of ACT on the primary and secondary outcome measures because our underlying model for treatment effectiveness is based on the assumption that ACT will prevent the development of PPSP by helping Veterans cope with postoperative pain. Therefore, receipt of surgery is inherent in our treatment model. Follow-up data on randomized subjects that did not have surgery will be included in a secondary analyses that will contrast the effect of ACT between those with and without surgery.

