For variables in the primary aim (pain severity and functioning), efficacy of ACT compared to AC at 6 weeks, 3 months and 6 months will be tested using linear mixed model analysis for repeated measures. The fixed effect in the model will include intervention group, time, and intervention*time interaction effect. The model will also include site, workshop (cluster) within intervention, and subject as random effects. Test of mean contrast will be used to compare between treatment group means and mean change from baseline to 6 weeks, 3 and 6-months post-TKA between ACT and AC. P-values will be adjusted using Bonferroni's method to account for the number of tests performed. The efficacy of ACT versus AC will be expressed as the group mean difference with a 95% confidence interval (CI), using the SAS STAT (14.1) MIXED procedure.

For the secondary aim (A), efficacy of ACT compared to AC on anxiety symptoms, depressive symptoms, pain acceptance, and engagement in values-based behavior will be compared using linear mixed model for repeated measures. Intervention group mean differences will be estimated and tested as described in the analysis for the Aim1 variables.

For the primary and secondary aim analyses, it is expected that randomization will lessen the need for covariate or moderator adjusted analyses. However, if any demographic, baseline, time from workshop to surgery, or perioperative variables (i.e. perioperative anesthesia/analgesic, postoperative complications, postop day 1 pain and function, etc.) are found to differ between intervention groups, the model will be expanded to include these variables as covariates or effect moderators to estimate and test intervention group mean differences, or odds ratio, controlling for these variables.

In addition to the analyses described above for the primary & secondary outcome measures, similar linear mixed model analyses that include all randomized subjects will be performed. This secondary analysis will include surgery status in the model to contrast the impact of the intervention on those with and without surgery.

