This study will use a cluster randomization approach where the unit of randomization will be the workshops. Randomization will occur right before each workshop so that all participants attending that workshop will be randomized to that intervention (i.e. ACT vs. AC). Statistician [name] will generate the randomization sequence to ensure adequate distribution of the two interventions over the study period. Randomization will be stratified by site (i.e. Iowa City versus Houston). The randomization sequence will be maintained by the Statistician in a password protected file. This file will be used to generate concealed envelopes maintained and accessed by a facilitator at each site. Allocation of workshop to intervention group will remain concealed for facilitators until approximately one week before the workshop to allow for the needed preparation. Workshop allocation to intervention group will remain concealed for all other study personnel and participants until the beginning of the workshop when all invited participants have arrived. Those in attendance will receive the assigned intervention. This allocation approach will eliminate pre-treatment withdrawals, minimize the potential for experimenter and participant bias by protecting the randomization sequence in a central location, maintain concealment of treatment allocation until the last possible moment, and keep the participants and outcome assessors blinded to treatment.

Virtual Workshops

The randomization scheme for BCM should be used for all virtual workshops.

Blinding

This is a double-blind study. Participants are blinded to which treatment is the treatment of interest and outcome assessors will be blinded to which treatment participants receive. The treatment allocators (i.e. project coordinators) and the workshop facilitators will not be blinded so they can be available throughout the study to answer questions regarding treatment. It is essential for them to know which group the participant is in, in case they need to troubleshoot the treatment.

Participants will complete the Workshop Usefulness Survey (Workshop Question 6wk) in REDCap at the end of their 6-week assessments and the Participant Blinding Question in REDCap at the end of their 6-month assessment. Assessors will complete the Assessor Blinding Question (Workshop Question 6mo) in REDCap at the end of each participants' 6-month assessment.

Post-Op Evaluations

6 Weeks, 3 Months and 6 Months Post-Op Surveys

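### Covariates are picked by between-arm tests and may include post-randomisation variables, while each outcome's own baseline is not a prespecified covariate

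*Combined protocol and SAP*

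**What the plan says.** All of this is in the Combined protocol and SAP.

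- **Data Analysis, opening paragraph.** The arms are compared variable by variable: "Variables will be compared across intervention groups using a t-test for continuous variables, Wilcoxon-rank sum test for ordinal and non-normally distributed continuous variables", with a chi-square test for categorical variables. Then: "Variables that are found to significantly differ between the groups will be used as covariates in the comparison of outcome measures". No significance level and no list of variables is given.
- **Data Analysis, paragraph on covariates for the primary and secondary aims.** A second rule applies "if any demographic, baseline, time from workshop to surgery, or perioperative variables" are seen to differ between arms. Its examples include anaesthesia and analgesia around surgery, complications after it, and pain and function on the first postoperative day. In that event "the model will be expanded to include these variables as covariates or effect moderators".
- **Data Analysis, primary aim.** "The fixed effect in the model will include intervention group, time, and intervention*time interaction effect". Site, workshop nested in arm, and participant are random effects. The contrasts are to "compare between treatment group means and mean change from baseline to 6 weeks, 3 and 6-months post-TKA between ACT and AC". The plan does not say which of the two, means or changes, is primary.
- **Randomization.** Workshops are the randomised units. "Randomization will be stratified by site (i.e. Iowa City versus Houston"). Under Virtual Workshops: "The randomization scheme for BCM should be used for all virtual workshops".
- **Pre-randomization assessment.** BPI, DASS-21, KOOS, CPAQ and CPVI are all collected before the workshop.

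**The concern.** For a variable fixed before a sound randomisation, a between-arm p-value describes the luck of the draw. It does not show whether the variable predicts the outcome, which is the reason to adjust for it. A rule built on such p-values leaves the main model unknown until the data are seen. Because the tests treat participants as independent, they will also trigger too often for any variable that clusters by workshop.

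The second trigger carries a different risk. Complications and first-day pain and function arise after the workshop, and the intervention could affect them. Conditioning on them can remove part of the treatment effect or introduce bias. The choice between covariate and moderator is also left open.

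Meanwhile the obvious prognostic candidate, the outcome's own baseline, is not a prespecified covariate. It is used only through change scores, and the two named contrasts can differ considerably in precision. Finally, a stratification factor with two levels is modelled as a random effect, so its variance must be estimated from two levels.

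**Working it through.** **Inputs from the Sample Size section:** difference 8 points on KOOS-ADL, SD 18, 6 participants per workshop, ICC 0.06, alpha 0.0167, power 0.80, 150 per arm. **Assumptions:** two-sided tests (sidedness is not stated); SD 18 is the SD at follow-up; the same design effect applies to every contrast; the baseline-to-follow-up correlation r, which the documents do not give, is 0.3, 0.5 or 0.7.

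**1. The plan's own figure.** Design effect = 1 + (6 − 1) × 0.06 = 1.30. With 25 workshops of 6 per arm, SE = 18 × √(2 × 1.30/150) = 2.37 and the noncentrality is 8/2.37 = 3.38. A cluster t-test on 2 × (25 − 1) = 48 df gives power 0.811; 24 workshops give 0.791. So 150 per arm is reproduced. Enrolment is 300/0.70 = 428.6, rounded to 430.

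**2. Three ways to use baseline.** Relative to a comparison of follow-up means, the variance is multiplied by 2(1 − r) for change scores and by 1 − r² with baseline as a covariate. The cluster t method is otherwise the same.

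| r | Variance factor, change | Variance factor, covariate | Power, follow-up means | Power, change | Power, covariate | n per arm for 80%: change | n per arm for 80%: covariate |
|---|---|---|---|---|---|---|---|
| 0.3 | 1.40 | 0.91 | 0.811 | 0.646 | 0.851 | 204 | 138 |
| 0.5 | 1.00 | 0.75 | 0.811 | 0.811 | 0.917 | 150 | 114 |
| 0.7 | 0.60 | 0.51 | 0.811 | 0.967 | 0.986 | 96 | 84 |

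Baseline as a covariate cuts the variance by r² against follow-up means (9%, 25%, 49%) and by (1 − r)/2 against change (35%, 25%, 15%).

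**3. How often the significance rule triggers by chance.** Assume a 0.05 level and independent variables.

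- With no clustering, the chance of at least one trigger is 1 − 0.95^10 = 40% for 10 variables and 1 − 0.95^20 = 64% for 20.
- If a variable has ICC 0.06, the unadjusted test statistic has variance 1.30. The per-test rate is then 2 × [1 − Φ(1.96/√1.30)] = 8.6%, giving 1 − 0.914^10 ≈ 59% and, for 20 variables, about 83%.

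The ICC of 0.06 is the plan's figure for the outcome. Using it for covariates is an assumption, and the zero-ICC figures are the lower end of the range.

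**4. Site as fixed or random.** This was simulated with 25 + 25 workshop means over two sites, 1,500 runs per scenario.

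| Site difference | Power, fixed site | Power, random site | Site variance estimated as zero |
|---|---|---|---|
| 0 points | 0.807 | 0.810 | 70% of runs |
| 3 points | 0.816 | 0.823 | 40% of runs |
| 9 points | 0.805 | 0.809 | 0.3% of runs |

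The variance is poorly estimated when the sites differ little, but power is the same to within one percentage point.

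**The case against.** The strongest reply is that the plan does use baseline. The aims are framed as change, change is one of the two contrasts, and baseline variables can be added if they differ. That stands: a reader might infer that baseline is ignored, and the documents do not support this. What is missing is a prespecified baseline covariate and a named primary contrast.

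A reader might also infer that a random site effect wastes power. The simulation shows no material loss, and a zero estimate does no harm when the sites do not differ. What stands is that a two-level stratification factor sits more naturally among the fixed effects.

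The power figures also invite objection.

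- The sample-size text calls the 8 points a change. If SD 18 is the SD of change, the change contrast has its planned power; baseline as a covariate would still reduce variance by 15% to 35% over the range of r.
- At r = 0.7 the gain over change scores is small.
- If baseline is a time level in the mixed model, random site and workshop intercepts cancel from the change contrast in complete data. The table therefore compares precision under a common design effect and does not give the power of the exact model.

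Nor need imbalance here be pure chance: the analysis set is limited to participants who had surgery, and facilitators learn the allocation about a week before the workshop. That is fair, but a significance filter neither detects nor repairs such selection reliably.

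Lastly, a reader might conclude that Iowa participants in virtual workshops will be analysed in the wrong stratum. The documents do not say how site will be coded, so this is an ambiguity to close.

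**Conclusion.** The plan should be changed on prespecification and precision. Covariate choice is data-driven through two separate rules. The first is likely to alter the model by chance: about 40% to 59% for 10 independent variables at an assumed 0.05 level, as the covariate ICC goes from 0 to 0.06. The second is the more serious in kind, because it admits variables that treatment may affect.

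Not prespecifying the outcome's baseline as a covariate gives up precision against either named contrast at each r examined. The amount depends on r, which the documents do not supply, and on reading SD 18 as the follow-up SD. Under those assumptions the largest gap is at r = 0.3 (0.646 for change against 0.851), and at r = 0.7 it is small (0.967 against 0.986).

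The random site term is a modelling weakness without material effect on power. A reader might take the low change-score power to mean that the trial is too small. That does not follow: 150 per arm reproduces from the plan's inputs and need not rise.

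**What to change.** 1. Delete both rules, the significance-test rule and the wider trigger based on observed differences, from the primary and secondary aim models.
2. For each outcome, prespecify as fixed effects its own baseline value and the stratum in which the workshop was randomised (Iowa list or Houston/BCM list, with virtual workshops under BCM), alongside arm, time and their interaction. The repeated outcome then consists of the three postoperative visits.
3. Keep workshop and participant as random effects.
4. Name one primary contrast: the baseline-adjusted difference between arms at each postoperative time point.
5. Confine variables that arise after randomisation to exploratory analyses, labelled as such.
6. Keep baseline tables descriptive, without tests.

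The cost is a change to the analysis text, made before unblinding. The outcome baselines are already collected and the allocation lists already exist; no extra participants are needed.

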Cut down, Annoyed, Guilty, and Eye-opener (CAGE).....	19
PTSD Checklist – short version (PCL-5).....	19
Data and Safety Monitoring (DSM) Plan.....	20
Monitoring Entity, Roles and Responsibilities	20
Roles of the SMC	20
Responsibilities of the SMC.....	20
Meetings of the SMC	21
Procedures for monitoring study safety, minimizing research-associated risk and protecting confidentiality of participant data	21
Procedures for Identifying, Reviewing, and Reporting Unanticipated Events	22
Compliance across Sites.....	23
Study Completion and Closeout Procedures	25

PRÉCIS

Short Title: Preoperative Pain and Rehab Education (PrePARE)

Objectives

[figure not shown]
Using a multi-site, double-blind, two-arm, parallel, randomized controlled trial with Veterans at-risk for PPSP post-TKA, the following aims will be addressed:

1. Primary Aim: To examine the superior efficacy of ACT versus Attention Control (AC) on postoperative pain intensity and functioning in at-risk Veterans undergoing TKA. Changes in pain intensity and functioning from baseline to 6 weeks, 3 months and 6 months post-TKA will be compared. Level of pain intensity will be measured using the BPI Pain Severity Subscale and level of functioning will be measured using the KOOS Activities of Daily Living and Quality Of Life Subscales.
2. Secondary Aims: A) To examine the superior efficacy of ACT versus AC on the severity of anxiety and depressive symptoms and improvements in coping skills. Changes from baseline to 6 weeks, 3 months and 6 months post-TKA will be compared. Anxiety and depressive symptoms will be measured with the Depression, Anxiety and Stress Scale (DASS-21). Coping skills (i.e. Pain Acceptance and Engagement in Values-Based Behavior) will be measured with the Chronic Pain Acceptance Questionnaire and the Chronic Pain Values Inventory. B) To evaluate whether decreases in distress-based symptoms and increases in coping skills mediate changes in pain and functioning at 6 months in Veterans receiving ACT. Changes in anxiety symptoms, depressive symptoms, pain acceptance and engagement in values-based behavior from baseline to 6 weeks and 3 months will be used as potential mediators for changes in pain and functioning at 6 months.

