For the exploratory aim, frequencies for each pharmacologic and non-pharmacologic pain management strategy will be calculated to describe the types of strategies reported at each visit. Patterns (from baseline to 6 months) and trends (i.e. changes over the 4 year data collection period) will be examined. Helpfulness ratings will be averaged using means and standard deviations or medians and interquartile ranges for each strategy to provide insights on strategies at-risk Veterans find helpful. Differences in types and helpfulness of pain management strategies by treatment group will be explored.

Sample Size

Sample size was estimated using KOOS-Activities of Daily Living Subscale (the primary outcome requiring the largest sample size). According to the literature, a change of 8 points or more represents a clinically significant improvement.⁸⁵ Therefore, assuming an average of 6 participants per workshop (cluster), with an ICC of 0.06 and a standard deviation of 18, a sample size of 300 Veterans (n=150 per treatment group) will be needed to detect a clinically

significant difference of 8 at a 0.0167 significance level (adjusted for testing at 3 time points) with 0.80 power. Assuming 20% will have surgery cancelled/postponed due to health issues and 10% will drop out after randomization (17% and 10%, respectively, was observed in our R34 study), we plan to enroll 430 Veterans to ensure that we will have $n=150$ per treatment group for the primary aim analyses. Veterans who do not have surgery after randomization will be followed over a similar timeframe and will be included in the secondary analyses.

Recruitment, Consent and Enrollment

Summary of recruitment and consent process, in-person

Identifying Patients

In order to increase awareness of the study, flyers describing the study will be posted in the orthopedics clinic and copies will be made available for patients to take. The study's Research Assistant (RA) will use Vista to identify all patients scheduled in the VAMC Orthopedics Clinic for a knee pain consultation. The RA will then review these patients' medical records to determine if they speak English with adequate competence AND do not have a diagnosis of dementia, bipolar or psychotic disorder, or history of brain injury. They will also review prior orthopedic notes to gauge readiness for surgery.

Approaching Patients

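### On the natural reading of the primary model, workshop clustering drops out of the change-from-baseline contrast, whose standard error is then too small

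*Combined protocol and SAP*

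**What the plan says.** The Objectives section words the primary aim as change: "Changes in pain intensity and functioning from baseline to 6 weeks, 3 months and 6 months post-TKA will be compared". The Data Analysis section gives a repeated-measures linear mixed model: "The fixed effect in the model will include intervention group, time, and intervention*time interaction effect". On the random part it says: "The model will also include site, workshop (cluster) within intervention, and subject as random effects". The contrasts are to "compare between treatment group means and mean change from baseline to 6 weeks, 3 and 6-months post-TKA between ACT and AC". Efficacy is then reported as a difference between groups with a 95% confidence interval, without saying whether the difference is in follow-up values or in change. The levels of time, any workshop-by-time term and the residual covariance are not stated.

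The Randomization section makes the workshop the unit: "This study will use a cluster randomization approach where the unit of randomization will be the workshops". On timing it adds: "Randomization will occur right before each workshop so that all participants attending that workshop will be randomized to that intervention". The section on post-consent screening and pre-randomization assessment has the baseline surveys finished before a participant is scheduled for a workshop. The Sample Size section allows for clustering, assuming 6 participants per workshop, "with an ICC of 0.06 and a standard deviation of 18".

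**The concern.** A random workshop intercept takes the same value at every visit in the model. If baseline is one of those visits, the intercept subtracts out of follow-up minus baseline, and so do the site and subject intercepts. The model then gives the difference in change no clustering term.

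The design points the other way. Baseline is measured before anyone has shared a workshop, so correlation produced by the same facilitators and the same group session can exist only afterwards. It stays in the observed change. The trial pays for clustering in its sample size, but the contrast that matches the wording of the primary aim would not carry it. At stake are the p-values and confidence intervals for change in pain and function, and for the secondary aim A outcomes, which use the same method.

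**Working it through.** **Inputs from the documents.** Difference 8, SD 18 (variance 324), ICC 0.06, 6 per workshop, significance level 0.0167 (taken as two-sided; the plan does not say), power 0.80, 150 per arm, and four visits (baseline, 6 weeks, 3 and 6 months).

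**Assumptions.** Baseline is a level of time. Workshop is an intercept only. All of the ICC arises after baseline. There are 25 full workshops of 6 per arm. The correlation ρ between visits, in the variance not due to workshop, is equal for all pairs. The documents do not give ρ, so I use 0.3 to 0.7.

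**1. The plan's own figure.** Without clustering, n = 2 × [18 × (2.393 + 0.842)/8]² = 105.95 per arm. The design effect is 1 + 5 × 0.06 = 1.30, and 105.95 × 1.30 = 137.7, so 138. With whole workshops and a t test on 2(k − 1) degrees of freedom, power is 79.1% at k = 24 (144 per arm) and 81.1% at k = 25 (150 per arm). The stated 150 is reproduced as 25 workshops of 6. Enrolment is 300/0.70 = 429, against 430 stated.

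**2. Variance components.** Workshop: σw² = 0.06 × 324 = 19.44. Remainder: 304.56. Residual: σe² = 304.56 × (1 − ρ).

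**3. What the planned model reports.** The intercepts cancel, which leaves 4 × (residual mean square)/n. A workshop effect present at three of four visits has the pattern 0, 1, 1, 1. Its sum of squares about its own mean is 0.75, and over 3 degrees of freedom that is 0.25. The residual therefore absorbs a quarter of σw², spread over n = 150 participants:

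model variance = 4(σe² + 0.25σw²)/150.

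**4. The actual variance** keeps σw² at the workshop level:

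true variance = 2(2σe²/150 + σw²/25).

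At ρ = 0.5, σe² = 152.28. Model: 4 × 157.14/150 = 4.190, SE 2.05. True: 2 × (2.0304 + 0.7776) = 5.616, SE 2.37.

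**5. Consequences.** Error = 2[1 − Φ(2.393 × ratio)]. Coverage = 2Φ(1.96 × ratio) − 1.

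| ρ | Model SE | True SE | Ratio | Error at nominal 1.67% | Coverage of a 95% interval |
|---|---|---|---|---|---|
| 0.3 | 2.41 | 2.69 | 0.90 | 3.2% | 92.1% |
| 0.5 | 2.05 | 2.37 | 0.86 | 3.9% | 91.0% |
| 0.7 | 1.60 | 2.00 | 0.80 | 5.5% | 88.4% |

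Simulation (8,000 null trials per setting) gave 3.3%, 3.7% and 6.0%. The chance of at least one false positive over the three visits was 8.0%, 8.9% and 12.7%, against a nominal 5%. A second simulation gave 2.6–4.0% for correlations of 0.3 to 0.6. Analysing change at workshop level brought the error back to 1.65–1.76% in the first simulation and about 1.4% in the second.

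**6. Link to the sample size.** At ρ = 0.5 the within-arm variance of change is 2 × 152.28 + 19.44 = 324, with 19.44/324 = 0.06 due to workshop. These are the sample-size inputs read as describing change. The true variance 5.616 equals 2 × 324 × 1.30/150. The model's 4.190, divided by 2 × 324/150 = 4.32, is an effective design effect of 0.97 in place of 1.30.

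**7. Sensitivity at ρ = 0.5.** With a post-baseline ICC of 0.01, 0.03, 0.06 or 0.10, the error is 2.0%, 2.7%, 3.9% or 5.7%. If workshops differ equally at baseline and follow-up, the cancellation is correct and the simulated error is 1.5%. An unstructured within-subject covariance with the same workshop intercept gives variance 2 × (2 × 152.28 + 19.44)/150 = 4.32, SE 2.08 and error 3.6%, so it does not repair the problem alone.

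**8. The other planned contrast.** For group means at 6 months the workshop variance is kept. At ρ = 0.5 the average model SE is 2.23 against an actual 2.34, with error 1.9%.

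**The case against.** The strongest reply is that the plan also tests group means at follow-up and lists them first. The sample size works as a plain comparison of two means with no pre/post correlation, which suits that contrast, and there the model is nearly right. This stands. It limits the problem to the change contrast, but does not remove it, because the primary aim is worded as change and nothing says which contrast decides.

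Second, the model form is partly inferred. The levels of time are not listed, and a workshop-by-time term is absent but not excluded. If change scores were the response, the workshop intercept would not cancel. This also stands, as a condition. A change-from-baseline contrast in a group-by-time model most naturally means that baseline is a level of time.

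Third, the plan does not say where the ICC of 0.06 comes from. Participants reach workshops by site, date and in-person or online mode, so some of it may be case mix already present at baseline, which cancels correctly. This reduces the error in proportion, as step 7 shows.

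Finally, a reader might infer that the subject intercept forces equal correlation between all visits and that the true error is therefore higher, at 5–6.5%. The documents do not support that. They state no residual covariance and give no visit correlations. It is also a separate matter: with essentially no workshop effect, correlations of 0.3 with baseline and 0.7 between follow-ups already give about 4.2–4.7% in simulation. What remains is conditional: if the subject intercept is the only within-subject structure and baseline correlates less with follow-ups than they do with each other, the standard error of change shrinks further.

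**Conclusion.** On the natural reading, the standard error of the difference in change omits clustering that arises after baseline. It is about 10–20% too small, and the two-sided error is about 3–5.5% at a nominal 1.67% (about 3.5–4% at correlation 0.5). This rests on baseline being a level of time, workshop being an intercept only, the whole ICC of 0.06 arising after baseline, and assumed equal visit correlations of 0.3 to 0.7.

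A reader might go further and infer that all primary inference is invalid, or that the sample size is wrong. Neither follows. The follow-up mean contrast is nearly correct, and the 150 per arm is reproduced. The fault is that the 1.30 design effect is not carried into the change contrast.

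**What to change.** Take the three post-operative visits as outcomes, with the baseline score as a covariate. Include a random workshop effect on those outcomes (or workshop-by-time), an unstructured within-subject covariance and Kenward-Roger degrees of freedom. If baseline must stay in the outcome vector, list it as a level of time and add a separate workshop random effect for the post-baseline visits. Name the deciding contrast, and apply the same text to secondary aim A.

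The cost is a few lines of analysis text and code, with no new data or participants. If the change contrast is kept, its intervals widen to their proper size, by a factor of 2.37/2.05 = 1.16 at ρ = 0.5. With baseline as a covariate, the variance under the same assumptions is 2[304.56(1 − ρ²)/150 + 19.44/25]. That gives standard errors of 2.29, 2.14 and 1.90 at ρ = 0.3, 0.5 and 0.7, each below the true standard error of change (2.69, 2.37 and 2.00). Precision is lost only against a figure that was too small.
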